### **Study Aims:**

1. Compare the cumulative incidence of glaucoma between the two treatment groups at age 10 years to determine which initial treatment is associated with the lowest long-term risk of glaucoma or glaucoma suspect.
2. Characterize myopic shift between the ages of 5 and 10 years in the IOL group.
3. Examine the impact of Unilateral Congenital Cataract on reading (speed, accuracy and comprehension), self-esteem and Health Related Quality of Life i

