### **Glaucoma**

At age 1 year we did not find a statistically significant difference in the percent of patients with glaucoma/glaucoma suspect between the IOL and CL treatment groups (16% vs 9%, respectively,  $p = 0.39$ , 95% CI for difference = 6% - 21%). At 5 Years, those numbers were higher (CL 35% and IOL 28%), but were still statistically equal. We hypothesize that newly diagnosed glaucoma/glaucoma suspect will occur more frequently between the ages of 5 and 10 years in the study eyes randomized to the CL group resulting in a higher cumulative incidence of glaucoma in this group. The percent of patients with glaucoma at 10 years of age will be compared between the treatment groups using Fisher's exact test. As described above under the statistical considerations for visual acuity, we expect very little missing data. We will conduct sensitivity analyses comparing results for patients examined at 10 years of age with results in which patients not examined at 10 years who did not previously have glaucoma will be assumed to either have or not have glaucoma at 10 years of age. Patients not examined at 10 year of age who were previously diagnosed with glaucoma will retain that diagnosis in the sensitivity analyses, since per the IATS protocol, once a patient is diagnosed with glaucoma the patient is considered to have glaucoma for the remainder of the study.

We expect that the percentage of patients with glaucoma in treated eyes will double between the age 1 and 10 year examinations in the CL group whereas the percent will remain largely unchanged in the IOL group.

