### **Statistical Analysis**

Descriptive analyses will be conducted to characterize the study population and detect potential selection bias as a result of missing data, dropouts or noncompliance/non-adherence. Two-sample t-tests will be used to compare continuous variables between two treatment groups. For continuous variables that are not normally distributed, appropriate transformations will be applied before normality-based tests are used or nonparametric tests such as Wilcoxon tests will be used as appropriate. Chi-square tests or Fisher’s exact tests will be used to compare categorical variables between groups.

All primary analyses will be intention-to-treat. The percent of patients with glaucoma/glaucoma suspect at 10 years of age will be compared between the treatment groups using Fisher’s exact test. We will also explore the role of baseline characteristics in the development of the primary endpoint using logistic regression and the Akaike information criterion (AIC; Akaike, 1974) will be used for model selection. In addition to analyzing the percent of patients who develop glaucoma/glaucoma suspect at any time up to age 10, we will also investigate analyzing the time to the primary endpoint using survival analysis methods, including the product-limit method to estimate the probability of developing glaucoma/glaucoma suspect versus time after surgery, comparing the time to developing glaucoma/glaucoma suspect between treatment groups with a log-rank test, and exploring the role of baseline characteristics with proportional hazards regression. The use of survival analysis methods may be problematic depending on how successfully we are able to determine the date of diagnosis, particularly for those patients who develop glaucoma/glaucoma suspect between 5 and 10 years of age when patients are not being examined within the study. Of note, patients not examined at 10 years of age who were previously diagnosed with glaucoma/glaucoma suspect will retain that diagnosis in all analyses, since per the IATS protocol, once a patient is diagnosed with glaucoma/glaucoma suspect the patient is considered to have glaucoma/glaucoma suspect for the remainder of the study.

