As secondary analyses, we will repeat the aforementioned analyses for the secondary endpoint of glaucoma. In addition, we will use logistic regression for a multinomial outcome (proportional odds models or baseline logic models) to analyze the three categories, Glaucoma, Glaucoma Suspect, and normal (not glaucoma/glaucoma suspect) jointly.

Linear mixed models (LMMs) will be used to characterize the change in refractive error over time for both the treated and fellow eyes in the IOL group and to compare the changes in the treated eyes of the two treatment groups. In addition, LMMs will be used to identify baseline risk factors such as age of cataract surgery and axial length and other factors that arise during childhood, such as amblyopia and glaucoma, that are associated with a larger than expected myopic shift in the IOL group.

We will use two approaches for handling missing data as needed. First, we will use the available-case approach (Little and Rubin, 2002), i.e., conducting the proposed analyses excluding patients for whom the glaucoma/glaucoma suspect status is not verified at 10 years. Second, we will use the approach of multiple imputation (Little and Rubin, 2002) before conducting the proposed analyses and we will also conduct sensitivity analysis (Little et al., 2012). In addition, to correct for potential selection bias as a result of non-adherence to patching in early years and/or having a secondary IOL in the CL group, we will use approaches including instrumental variable and propensity scores (Little et al., 2009; Rosenbaum and Rubin, 1983). In addition, in case there are deviations from the target date for the outcome measurement, we will adjust for the time of the outcome measurement in our analyses as appropriate.

In addition to development of glaucoma, other clinical outcomes will also be measured and the analysis methods to be used in describing those outcomes are as follows.

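### The carry-forward and available-case rules, applied together, keep unexamined cases but drop unexamined non-cases; the effect is small, the Glaucoma section conflicts with it, and the have/not-have check lacks opposite-arm extremes

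*Combined protocol and SAP*

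**What the plan says.** Aim 1 compares cumulative incidence at age 10 "to determine which initial treatment is associated with the lowest long-term risk of glaucoma or glaucoma suspect". Under Statistical Analysis (Chapter 5), glaucoma/glaucoma suspect is the primary endpoint, compared by Fisher's exact test, and glaucoma alone is secondary. Four statements bear on children not seen at 10 years:

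- **Carry-forward, Statistical Analysis:** "patients not examined at 10 years of age who were previously diagnosed with glaucoma/glaucoma suspect will retain that diagnosis in all analyses".
- **Missing data, Statistical Analysis:** "We will use two approaches for handling missing data as needed". The first is available-case, meaning "conducting the proposed analyses excluding patients for whom the glaucoma/glaucoma suspect status is not verified at 10 years". The second is multiple imputation, with a further sensitivity analysis whose content is not given. Neither approach is named as primary.
- **Glaucoma section, Chapter 5:** results for children examined at 10 years are compared with scenarios in which "patients not examined at 10 years who did not previously have glaucoma will be assumed to either have or not have glaucoma". Here carry-forward is stated for the sensitivity analyses only. The section adds that "we expect very little missing data".
- **Phase 3 Definition and Diagnosis of Glaucoma, Chapter 1:** medical records are to be reviewed for every patient, so some unexamined children may still have their status verified.

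On time to diagnosis, the plan says "we will also investigate analyzing the time to the primary endpoint using survival analysis methods", and warns that diagnosis dates between 5 and 10 years may be hard to establish.

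**The concern.** If prior diagnoses are carried forward in every analysis, that includes the available-case analysis. An unexamined child with a 5-year diagnosis then counts in numerator and denominator, while an unexamined, unverified child without one leaves the denominator. Whether a child is included depends on the outcome, so the proportion can be wrong even when visits are missed for reasons unrelated to glaucoma. That proportion is the quantity in Aim 1.

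The have/not-have check is meant to show how far missing children could change the result. It names no arm. On its natural reading both arms are filled in the same way, so it never tries the case in which the missing children differ by arm, which is the case that threatens a comparison. It also refers to glaucoma, whereas the primary endpoint is glaucoma/glaucoma suspect.

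**Working it through.** **Inputs.** There are 114 children, 57 of them CL (Study Design, Chapter 5), hence 57 IOL. The 5-year rates of glaucoma/glaucoma suspect are CL 35% and IOL 28% (Glaucoma section), which fit 20/57 = 35.1% and 16/57 = 28.1%; the counts are inferred. The plan gives no 10-year missing-data figure, so the missing rates are assumed. Retention so far is 99%, with one child lost at the 5Y visit (Retention; Performance of Individual Sites). New cases among 5-year non-cases are assumed at q = 20%, range 10 to 30%.

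**Check of arm sizes and test.** The plan has no figure for the effect examined here. For 1 year it gives 16% v 9%, p = 0.39. Fisher's test on 9/57 v 5/57 gives 0.393, which agrees.

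**Bias of the combined rule.** Let a be the 5-year cases, n0 = 57 − a, and m the share of 5-year non-cases left unexamined and unverified, unrelated to outcome.

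- True proportion: (a + q·n0)/57. For CL, (20 + 7.4)/57 = 48.1%. For IOL, (16 + 8.2)/57 = 42.5%.
- Available-case with carry-forward: [a + q·n0(1−m)] / [a + n0(1−m)]. For CL at m = 5%, (20 + 7.03)/(20 + 35.15) = 49.0%, an excess of 0.94 points.

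| m | CL excess (points) | IOL excess (points) | Shift in arm difference (points) |
|---|---|---|---|
| 1% | 0.18 | 0.16 | 0.02 |
| 5% | 0.94 | 0.84 | 0.10 |
| 10% | 1.95 | 1.74 | 0.21 |
| 20% | 4.19 | 3.77 | 0.41 |

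The 10% and 20% rows are stress values that the documents do not support. At 5%, q = 10 to 30% gives 0.8 to 1.1 (CL) and 0.7 to 0.9 (IOL). If records review verifies half of the unexamined non-cases, 5% unexamined gives about 0.5 and 0.4.

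For the arm difference, the plan expects new cases in CL "whereas the percent will remain largely unchanged in the IOL group". With q = 20% in CL and 0 in IOL, equal loss shifts the difference by −0.11 points at 5% and −0.53 at 20%. An assumed unequal loss of 10% v 5% shifts it by +1.1 (more lost in CL) or −0.8 (more lost in IOL) at q = 20% in both arms.

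**Cause.** If unexamined prior cases were dropped at the same rate, numerator and denominator would both be multiplied by (1−m) and the bias would be 0. If all 57 are kept and missing non-cases are filled in at rate q, it is also 0. The asymmetry is the source.

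**Direction.** The full-set proportion is a weighted average of the retained-set proportion and the incidence among dropped children. The retained figure is too high exactly when the dropped children's incidence is below it. In the 5% example the dropped incidence is 20%, against retained figures of 49.0% (CL) and 43.3% (IOL).

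**Have/not-have check.** Illustration with assumed counts: 28 CL v 16 IOL known cases, a few unverified non-cases in each arm, two-sided Fisher, assumed level 0.05.

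| Result | 1 per arm | 3 per arm |
|---|---|---|
| Available-case | 0.033 | 0.031 |
| Both arms not have | 0.034 | 0.034 |
| Both arms have | 0.035 | 0.037 |
| CL not, IOL have | 0.055 | 0.128 |

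With equal numbers missing, the completed-table difference is the same in both planned scenarios: (28 − 16)/57 = 21.1 points. They therefore say little about sensitivity of the difference.

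**The case against.** The strongest objection is textual. The Glaucoma section's base comparison is of children examined at 10 years, with carry-forward confined to the sensitivity analyses. Read that way, unexamined children of both kinds leave the base analysis and there is no bias from the rule. This stands: the text supports a conflict between two sections, with a bias on one reading. It does not establish that the trial's result will be biased.

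Second, the effect is negligible at the retention reported so far. At 1% missing it is about 0.2 points, against 1/57 = 1.75 points for one child, and records review should reduce it further. This also stands. Five years without study examinations mean that earlier retention is no guarantee, but the documents give no ground for expecting heavy loss.

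Third, if unverified non-cases remain in one arm only, have and not-have already cover both extremes. True; the added scenarios matter only when both arms have such children.

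Fourth, multiple imputation and a further sensitivity analysis are already planned. Imputation does remove the asymmetry, but the plan does not say which approach leads, and the content of the sensitivity analysis is not stated.

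A reader might infer that the available-case result is the primary one because it is listed first. The plan does not rank the two. A reader might also infer that the 20% new-case assumption leads to a borderline arm difference. It gives about 27 v 24 cases, p = 0.71. A borderline 27 v 16 needs the further assumption of no new IOL cases, and there the planned scenarios already exceed 0.05 (0.053 and 0.058 with 3 per arm).

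**Conclusion.** The point holds in a limited form and is minor. Followed literally, the two rules under Statistical Analysis make inclusion depend on outcome. The available-case 10-year proportion is then too high if visits are missed at random, and more generally whenever incidence among the dropped children is below the retained proportion. The overstatement is about 0.2 points per arm at 1% missing and 0.8 to 0.9 at 5%, given the inferred 5-year counts and 20% new cases.

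The stronger reading, that the comparison of treatments is distorted, is not supported: equal loss up to 20% moves the difference by at most about 0.5 points. Nor is the upward direction unconditional, since it would reverse if the dropped children had a higher incidence than those retained.

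The gap in the have/not-have check is real on its natural reading. The 28 v 16 example shows that a result can pass every planned version and fail one opposite-arm extreme. It says nothing about how likely that is.

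**What to change.** 1. Reconcile the Glaucoma and Statistical Analysis sections to one rule that treats unexamined prior cases and non-cases alike.
2. For the reported incidence and the arm comparison, use all 114 children as randomised. Carry prior diagnoses forward, use records-verified status where it exists, and apply the planned multiple imputation to the remaining unverified non-cases.
3. If an available-case result is also shown, select children by 10-year examination or verification whatever their prior diagnosis. Otherwise label it as biased upward under random missingness.
4. State that the have/not-have check applies to glaucoma/glaucoma suspect, and run Fisher's test on the completed 57 v 57 tables. Add the two opposite-arm scenarios: CL have with IOL not, and CL not with IOL have.

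The cost is SAP wording and a little programming, with no new data. The downside is slight dependence on the imputation model, which is small if as few children are missing as the plan expects. Leading with imputation is partly a matter of preference at such low loss; a symmetric rule and a check aimed at the primary endpoint are the essential parts.

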## **CHAPTER 5 STATISTICAL CONSIDERATIONS & DATA CAPTURE AND MANAGEMENT**

### **Study Design**

IATS is a randomized controlled clinical trial with patients originally assigned to either CL or IOL as a correction for aphakia after cataract surgery. During Phases 1 and 2, investigators diligently avoided implanting a secondary IOL in patients randomized to CL correction except when it would be in the best interest of the child to have a secondary IOL because of lack of compliance with CL correction. Steering Committee approval was required before a secondary IOL could be implanted and documentation of the efforts to improve CL compliance had to be submitted before approval was granted. No child randomized to CL received a secondary IOL before the vision test at 12 months of age. As of December 2013 when all 57 study participants who were randomized to CL completed the study, only 3 had received a secondary IOL before the 5Y visit. Since the 5Y visit, 16 children in the CL group have received secondary IOLs.

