**Visual Acuity:** For visual acuity at 10 years of age, we intend to use the Wilcoxon rank-sum test to compare the median visual acuities of the two treatment groups, with the patients included in the treatment group to which they were randomly assigned (intention-to-treat). As described in the section above (Status of Patients between Phases 2 and 3), among the patients randomized to CL who have thus far completed the 5 year of age exam, 38% have had secondary IOL implantation (insertion of an IOL after the initial cataract surgery). Thus, unlike in Phase 1 (1 year of age) when none of the contact lens patients had a secondary IOL and in Phase 2 (5 years of age) when only 2 contact lens patients had received a secondary IOL, for Phase 3 (10 years of age), a substantial percent of the patients in contact lens group will have a secondary IOL. Therefore, for visual acuity at 10 years of age, IATS will be a comparison between one treatment in which patients have an IOL inserted at the time of the cataract surgery and a second treatment in which patients are initially treated with a contact lens with the option of implanting a secondary IOL after 5 years of age. Analyses that attempt to address the question of a secondary IOL versus no IOL would likely be fraught with bias. Although the decision to have a patient undergo secondary IOL implantation is largely one of physician and parental preference, the condition of the patient is also a factor. For example, a secondary IOL would not be implanted in a patient with extremely poor vision. Therefore, such comparisons will be avoided.

In addition to the analysis to compare visual acuity at age 10 between the treatment groups, we will also investigate the relationship between baseline factors and the visual acuity at age 10. Since as described above we expect that visual acuity at age 10 will be skewed, for the multivariate analyses using linear regression, we will explore transformations of visual acuity to a less skewed distribution that also addresses the issue of lower threshold values for patients with extremely poor vision. Another approach we will investigate is categorizing visual acuity into 2 categories depending on whether or not the patient's vision is within normal limits (Driver et al., 2008) and using logistic regression to evaluate the relationship with baseline characteristics.

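### Does the plan to correct for secondary IOLs by instrumental-variable and propensity methods conflict with a comparison by initial treatment?

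*Combined protocol and SAP*

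**What the plan says.** Aim 1 in Study Aims is to "determine which initial treatment is associated with the lowest long-term risk of glaucoma or glaucoma suspect". Statistical Analysis in Chapter 5 makes intention-to-treat the rule for primary analyses, with Fisher's exact test on the proportion with glaucoma or glaucoma suspect at age 10. A diagnosis, once made, is kept for the rest of the study.

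Later in that section, after the handling of missing glaucoma status, the plan adds supplementary methods "to correct for potential selection bias as a result of non-adherence to patching in early years" and/or from "having a secondary IOL in the CL group, we will use approaches including instrumental variable and propensity scores". The sentence itself does not name glaucoma. Its place in the section makes glaucoma the likely target.

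The Visual Acuity paragraph of the same section describes the CL group at age 10 as patients "initially treated with a contact lens with the option of implanting a secondary IOL after 5 years of age". It then says: "Analyses that attempt to address the question of a secondary IOL versus no IOL would likely be fraught with bias". It concludes: "Therefore, such comparisons will be avoided". Both the description and the avoidance are written for visual acuity.

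The counts of early secondary implants differ. Visual Acuity says that by Phase 2 "only 2 contact lens patients had received a secondary IOL", whereas Study Design in Chapter 5 says "only 3 had received a secondary IOL before the 5Y visit".

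**The concern.** Three things look wrong on a first reading.

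- **The question.** If Aim 1 is about initial treatment, a secondary IOL is something that happens within the CL strategy. To call it a bias needing correction is to change the question. The acuity paragraph appears to recognise this, and the glaucoma text does not.
- **Time order.** Most secondary implants came after the 5-year visit, but many CL diagnoses came before it. A comparison of implanted with non-implanted CL eyes that ignored dates would charge earlier diagnoses to a later operation, or credit the operation with their absence.
- **Interpretation.** A result presented as corrected for selection bias could be read as a better answer to Aim 1 than the intention-to-treat result. If arm is the instrument, it also assumes that a late implant acts like one placed in infancy. Glaucoma Evaluation in Chapter 1 gives reason to doubt this: it suggests that implantation at the infant operation may cause early glaucoma through added surgical trauma.

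At stake is how a supplementary estimate is read. The primary test is not affected.

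**Working it through.** **Inputs.** CL arm 57 (Study Design); IOL arm 114 − 57 = 57. Secondary IOLs in the CL arm: 3 before the 5-year visit and 16 since (Study Design), or 38% overall (Visual Acuity). Glaucoma or suspect by 5 years: CL 35%, IOL 28% (Glaucoma section, Chapter 5).

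**1. Check the base.** The 1-year rates of 16% and 9% fit 9/57 and 5/57. Fisher's exact p = 0.393 agrees with the stated 0.39, so 57 per arm is sound.

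**2. Five-year counts.** 0.35 × 57 = 20.0 and 0.28 × 57 = 16.0, so 20 v 16 (Fisher p = 0.55). Using 5 CL cases at 1 year plus the 16 new cases in the Introduction gives 21 in place of 20.

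**3. Time order.** 20 − 3 = 17, so at least 17 of the CL diagnoses at 5 years cannot follow a secondary IOL. The documents do not say how many of the 16 later implants went into eyes already diagnosed. A proportional share would be 16 × 20/57 = 5.6. Examples of the gap at 5 years, before any of those implants could act:

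| Later implants in diagnosed eyes | Later-IOL eyes | Other CL eyes | Gap (points) |
|---|---|---|---|
| 0 | 0/16 = 0% | 20/41 = 49% | −49 |
| 6 | 6/16 = 38% | 14/41 = 34% | +3 |
| 10 | 10/16 = 62% | 10/41 = 24% | +38 |

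An ever/never contrast with no dates could therefore mislead in either direction. The plan does not propose that contrast.

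**4. Arm as instrument (an assumption; none is named).** Treating the IOL arm as fully exposed, the simple ratio estimate is the intention-to-treat difference divided by (1 − u), where u is the share of the CL arm with a secondary IOL. The 5-year difference is 20/57 − 16/57 = 7.0 points, SE 8.7, 95% CI −10.0 to 24.0.

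| u | Multiplier | Estimate | 95% CI |
|---|---|---|---|
| 19/57 = 33.3% | 1.50 | 10.5 | −15.0 to 36.1 |
| 38% | 1.61 | 11.3 | −16.1 to 38.8 |

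Difference and SE scale together, so z = 7.0/8.7 = 0.8 throughout. This illustrates the scaling on 5-year rates. I do not project to age 10, because the later conversion rates would have to be invented.

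**5. Size of the timing effect in that estimate.** The 5-year difference arose when u was at most 3/57, a multiplier of 1/(1 − 3/57) = 1.06. Multiplying it by the later figure adds 7.0 × (1.50 − 1.06) = 3.1 points, or 7.0 × (1.61 − 1.06) = 3.9 at 38%. The half-width of the rescaled interval at 1.50 is 17.0 × 1.50 = 25.5 points.

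**6. The uptake figures.** (3 + 16)/57 = 33.3%, or (2 + 16)/57 = 31.6%. No whole number out of 57 rounds to 38%, but 19/50 does. Visual Acuity gives its percentage for those who had so far completed the 5-year examination, so a different data cut is plausible though not shown. A different cut might also explain 2 v 3.

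**The case for a change.** The best case for a change is that a few sentences would remove any risk of misreading, at no cost in data. The reason given for caution with acuity, that the patient's condition influences the decision to implant, also threatens a propensity analysis of glaucoma, which needs no unmeasured confounding. The plan never says why the caution would lapse. The paragraph on adverse events applies the glaucoma methods to other events, so loose wording could spread.

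Much of this stands as a comment on wording. Speaking of correcting a bias is inexact beside Aim 1, and the assumptions are unstated. But the apparent conflict shrinks on inspection. The acuity paragraph limits its definition and its avoidance rule to acuity, and its example, that an eye with extremely poor vision would not receive an implant, is about acuity. An intention-to-treat primary analysis with a supplementary noncompliance analysis is ordinary practice.

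The technical objections depend on guesses. A comparison of implanted with non-implanted CL eyes is not in the plan, and propensity scores could equally serve a between-arm comparison. Arm is a natural candidate instrument for IOL exposure, but the same sentence also covers patching, for which arm is not an evident instrument, and one binary instrument cannot separate two exposures. Nor does the plan limit itself to an unadjusted ratio. Timing is already in view: the record review in Phase 3 Definition and Diagnosis of Glaucoma is meant to establish age at onset, operative reports are collected, and Statistical Analysis warns that dates of diagnosis may be uncertain.

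**Conclusion.** No change to the plan follows. Aim 1 is answered by the intention-to-treat comparison, which none of this touches. The instrumental-variable and propensity work is non-primary by the plan's own rule, and what is missing is detail that an analyst can settle sensibly when that work is done: report it beside the intention-to-treat result, state its assumptions, and respect the order of operation and diagnosis. No stated rule has been shown to give a wrong result.

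The sizes support this. With arm as instrument, an unadjusted estimate is the intention-to-treat difference times 1.50 to 1.61 with the same z, and the part due to timing, 3 to 4 points on the 5-year rates, is small against a half-width of about 25 points. The ever/never gaps of −49 to +38 points are large, but they belong to an analysis the plan does not state.

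The differing figures (2 v 3 early implants; 38% v 33%) are a clerical matter or different data cuts and do not enter the primary analysis.

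The conclusion rests on 5-year counts worked back from rounded percentages, on the IOL arm being treated as fully exposed, and on the supplementary sentence being read as directed at glaucoma.
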